9.5 SAMPLE SIZE CONSIDERATIONS

Presentation of sample size in this study is based on demonstrating STA® - Liatest® D-Di XL effectiveness in "unlikely" subjects for VTE meets the following performance goals as provided in Table 1A of CLSI guideline (H-59A p. 28):

- Sensitivity

³ U.S. Dept. of HHS, FDA. Guidance for industry: E9 statistical principles in clinical trials. 1998; Section 5.2.1, pp. 28 –

- Lower 95% two-sided confidence interval (LCL) ≥ 0.90
- Point Estimate ≥ 0.95
- NPV
 - LCL 95% two-sided ≥ 0.95
 - Point Estimate ≥ 0.97

While performance goals (PGs) are the same for PE and DVT, power must be calculated separately for each because of different prevalence and accuracy assumptions for PE+ and DVT+. The accuracy assumptions are based on observed results in the studies submitted to FDA⁴. Notwithstanding, blind sample size re-estimation (i.e. counting of positive cases during the trial) will be employed to achieve requisite power. For both PE and DVT sample sizes we assume that at about 70% of reference-positive cases will be from the US and the rest (about 30%) from out of US (OUS).

PE: Power for Meeting PGs

Presentation of sample size is based on obtaining a enough reference-positive cases to achieve 90% power to meet the LCL PG for sensitivity (≥ 0.90), which will necessarily:

- Enable success on the point estimate PG for sensitivity, since the minimum true-positive rate needs to meet the LCL PG, given the sample size reported below, is the same as the minimum needed for the point estimate PG.
- Yield enough reference-negative patients for near 100% power to meet the PGs for NPV, due to low prevalence of positive cases.

Based on the counting of positive cases (allowed by this protocol) to the date of amendment V2.1, we assume:

- US prevalence of reference-positive = 3.4%
- OUS prevalence of reference-positive = 5.7%

Based on historical data, we assume:

- D-Di XL sensitivity = 98%
- D-Di XL NPV = 99.6%

Given the above, N = 115 reference-positive subjects are needed to have at least 90% power to demonstrate efficacy on both sensitivity and NPV⁵. Given at least N = 75 in the US (65%), 2,206 “unlikely” US subjects will be needed (75/0.034). Given N = 40 OUS (35%) at most1, 702 “unlikely” OUS subjects will be needed (40/0.057).

⁴ In these studies, DVT results demonstrate higher accuracy parameters than PE. For the purpose of computing power in this study we assume the PE accuracy observed for both indications.

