9.6 STATISTICAL ANALYSIS

Overview

The data will be summarized in tables listing the mean, standard deviation, median, minimum, maximum and number of subjects for continuous data or in tables listing count and percentage for categorical data, where appropriate. Data listing by subject will be provided.

The effects of noncompliance, dropouts, and possible covariates, will be assessed to determine the impact on the general applicability of results from this study.

All statistical analyses will be performed and data appendices will be created using the SAS® system.

Subject Disposition

Subject disposition will be tabulated; the number of enrolled, exposed, prematurely terminated and completed subjects will be summarized overall and by Device status.

A list of dropouts will be prepared including reason for discontinuation, and time of discontinuation.

Primary Analysis

Primary analysis will be conducted using Primary efficacy analysis set and will be done separately for PE and DVT.

Co-primary Analysis I

NPV will be computed in the usual manner as follows:

$$NPV = TN / (TN + FN)$$

Where,

TN = No. of true negative subjects

FN = No. of false negative subjects

We will test NPV using the following hypotheses:

$$H_0: NPV \leq 0.95$$

$$H_1: NPV > 0.95$$

An exact binomial confidence interval will be used, where success will be declared if the two-sided 95% LCL is at or above the PG specified.

Additionally, we require: Point estimate of $NPV \geq 0.97$.

Co-primary Analysis II

Sensitivity will be computed in the usual manner as:

$$Sensitivity = TP / (TP + FN)$$

Where,

TP = No. of true positive subjects

FN = No. of false negative subjects

We will test Sensitivity using the following hypotheses:

H_0 : Sensitivity ≤ 0.90

H_1 : Sensitivity > 0.90

An exact binomial confidence interval will be used, where success will be declared if the two-sided 95% LCL is at or above the PG specified.

Additionally, we require: Point estimate of Sensitivity ≥ 0.95 .

Success for DVT will be declared if the four DVT PGs have been met.

Success for PE will be declared if the four PE PGs have been met.

Covariate Analyses, Including Poolability

The effect of the following covariates will be examined on Device accuracy:

- Age (measured continuously),
- Gender,

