- Sites within US and OUS separately (enrolling sites with at least 20 subjects will be included separately. Sites with a smaller number of subjects will be combined into a single, "other" site). This is a test of site poolability within US and OUS separately.
- Region (US, OUS), which is a test of poolability of the US and OUS populations,
- PTP (measured by validated and standardized test).

Effect of covariates will be assessed for each covariate individually using the following logistic regression model:

Device = Cov + Reference Standard + Cov*Reference Standard

Where,

Device – D-dimer XL result (dichotomous)

Reference Standard – Diagnosis by imaging or follow-up (dichotomous)

Cov – Relevant covariate (categorical or continuous, depending on covariate)

Additional potential covariates will be compared between US and OUS and, if found significant, will be analyzed using the model described above.

In this model we are interested in the Cov*Reference interaction, whereby a significant result indicates that Device performance relative to Reference Standard is affected by the covariate.

Secondary Analysis

The following will be provided for Primary analysis sets:

- Specificity,
- Positive Predictive Value,
- Positive and negative likelihood ratios.
- Prevalence of reference positive cases

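### The US/OUS poolability analysis in section 9.6 is never adjusted for the case-mix imbalances that the same section screens for; the practical gap is in the comparison of specificity

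*Combined protocol and SAP*

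**What the plan says.** All of this is in protocol section 9.6, under the covariate and poolability heading. The listed covariates are age, gender, sites within US and OUS, Region and PTP. On how they enter the model: "Effect of covariates will be assessed for each covariate individually using the following logistic regression model". The model is "Device = Cov + Reference Standard + Cov*Reference Standard", so it holds one covariate at a time. Region is listed as "Region (US, OUS), which is a test of poolability of the US and OUS populations".

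The section then adds a screen for imbalance: "Additional potential covariates will be compared between US and OUS and, if found significant, will be analyzed using the model described above". The model described above is the one-covariate model, so a covariate that differs by region is examined alone, without Region.

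The term that is read is the interaction: "In this model we are interested in the Cov*Reference interaction". A significant result is taken to mean that the covariate affects device performance relative to the reference. No significance level is given for this term, and nothing is said about what follows if it is significant.

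No section of the supplied text puts Region and another covariate into one model or stratifies the Region comparison. Section 9.1 refers to separate PE and DVT SAPs, to be signed before the first data lock. Their content is not in the supplied text.

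**The concern.** The main reason to look for covariates that differ between US and OUS is to learn whether such differences produce, or conceal, a regional difference in accuracy. The plan runs the screen but does not carry its result to the Region comparison. If OUS patients are older, for example, and age raises D-dimer in patients without VTE, specificity will look lower OUS although the assay behaves identically. Conversely, a true regional shift (laboratory, analyser, population) can be cancelled by case mix and go unseen. With one-covariate models, a finding for Region cannot be separated from a finding for age or PTP when these vary together.

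At stake are the interpretation of the regional comparison and of specificity, which is a secondary objective (section 3.2), and the statement on general applicability that section 9.6 promises.

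**Working it through.** PE is used because its regional counts are internally consistent. For DVT, 69/0.053 = 1,302, whereas section 9.5 prints 1,032.

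**Inputs from section 9.5 (PE).** 75 US and 40 OUS reference-positives; prevalence 3.4% US and 5.7% OUS; sensitivity 98%.

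**Reproducing the plan's figures.** 75/0.034 = 2,206 and 40/0.057 = 702, total 2,908, as stated. Reference-negatives: 2,206 − 75 = 2,131 US and 702 − 40 = 662 OUS. With 115 positives, the exact lower limit is 0.9015 at 110 true positives and 0.890 at 109, so at most 5 false negatives are compatible with success. Power at 98% sensitivity is 97.1%, which satisfies "N = 115 reference-positive subjects are needed to have at least 90% power".

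**Step 1: information in the term the plan reads.** Expected false negatives are 75 × 0.02 = 1.5 US and 40 × 0.02 = 0.8 OUS. Fisher exact power for a regional sensitivity difference, with US at 98%, is 13% if OUS is 95%, 48% if 90% and 76% if 85%. The positives' contribution to the variance of the Region-by-Reference coefficient is 1/(75 × 0.98 × 0.02) + 1/(40 × 0.98 × 0.02) = 0.680 + 1.276 = 1.956, so the SE is about 1.40.

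**Step 2: assumptions for an illustration.** None is in the documents: age SD 16 years; odds of a positive D-Di XL result up 4% per year (log-odds 0.0392); overall US specificity 50%; OUS patients older by 3, 6 or 9 years; two-sided 5% level.

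**Step 3: unadjusted specificity contrast in reference-negatives.** Averaging the logistic curve over the age distribution gives OUS specificity and the apparent regional log-odds ratio b. With p the proportion device-positive among reference-negatives, SE = √[1/(2,131 p_US(1−p_US)) + 1/(662 p_OUS(1−p_OUS))], and the rejection rate is Φ(b/SE − 1.96) plus a negligible lower tail.

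| Age gap, no device difference | OUS specificity | b | SE | Rejected, unadjusted |
|---|---|---|---|---|
| 3 years | 47.3% | 0.108 | 0.089 | 23% |
| 6 years | 44.6% | 0.216 | 0.089 | 68% |
| 9 years | 42.0% | 0.324 | 0.090 | 95% |

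Repeated simulation of this set-up (400 to 1,500 trials per scenario) gave 22–23%, 63–71% and 94–96% unadjusted, and about 3–6% after adjustment for age. With a true OUS shift of −0.25 log-odds and a 6-year gap, the two effects cancel (b = −0.01, OUS specificity 50.3%). The shift was found in about 5% of trials unadjusted and 73–77% adjusted.

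**Step 4: the same scenarios on the plan's Region-by-Reference term.** If age acts only in reference-negatives, the 6-year gap biases the coefficient by about −0.22 (ratio 0.80), or 0.22/1.40 = 0.15 SE. If age acts equally in positives and negatives, the bias is about +0.02. Simulated likelihood-ratio rejection rates with age acting in negatives only (600 trials per scenario) were:

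| Scenario | Unadjusted | Adjusted |
|---|---|---|
| Gap 0 years | 5.8% | 6.3% |
| Gap 3 years | 6.0% | 6.0% |
| Gap 6 years | 7.3% | 7.0% |
| Gap 9 years | 5.7% | 5.8% |
| Gap 6 years, true shift −0.25 | 6.0% | 6.5% |

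The differences are within simulation error. The confounding in step 3 is therefore real for specificity but is swamped by sampling noise in the interaction term.

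**The case against.** The strongest case against is that the planned test is hardly harmed. Its decision term is the interaction, and step 4 shows that adjustment leaves its rejection rate where it was. This stands. The percentages in step 3 illustrate a specificity contrast that the plan does not test; they are not error rates of the plan's interaction test.

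A reader might infer that confounded poolability undermines the pooled sensitivity and NPV on which success rests. The documents do not support that. Section 9.6 judges each co-primary on its own limit ("success will be declared if the two-sided 95% LCL is at or above the PG specified") plus a point estimate, and declares success for an indication when its four performance goals are met. Nothing makes success conditional on the Region test.

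A reader might also take the prevalence figures (PE 3.4% against "OUS prevalence of reference-positive = 5.7"%; DVT 5.3% against 8.1%) as proof of confounding. The model conditions on the reference result, so prevalence is not itself a confounder. It is only indirect evidence that case mix may differ. The documents give no age, gender or PTP distribution by region, and the screen may find nothing.

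Finally, an unadjusted Region comparison answers a legitimate question, whether accuracy differs between the populations as recruited, and the separate SAPs may already contain a joint model. Both points stand. They do not remove the gap in section 9.6: it asks which covariates differ by region and then makes no use of the answer in the regional comparison.

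**Conclusion.** The point holds in a limited form. As written, section 9.6 cannot say whether case mix explains or hides a regional difference in device performance. For sensitivity this matters little in practice, because about 2 expected false negatives leave almost no information with or without adjustment. For specificity, with about 2,800 PE reference-negatives (2,131 + 662 = 2,793), it can matter a great deal: under the stated assumptions, a 6-year age gap produces a spurious contrast in about two thirds of trials, or reduces detection of a real shift from about three quarters to 5%. Those sizes depend entirely on the assumed age gap, slope, SD and specificity, and a 3-year gap gives 23%. The primary analyses, the sample size and the success rule are unaffected. This is a worthwhile improvement to a supportive analysis, not a flaw in the confirmatory tests.

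**What to change.** In section 9.6, or in the PE and DVT SAPs before they are signed:

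- Keep the one-covariate models and label them descriptive.
- Add a pre-specified US–OUS difference in specificity among reference-negatives with its 95% CI, unadjusted and adjusted for age, gender, Wells PTP and any additional covariate found to differ by region (for example, a logistic model with Region and these covariates, standardised to the pooled population).
- In reference-positives, report sensitivity by region with exact intervals instead of fitting a full joint model. For example, one false negative in each region would give 74/75 (92.8% to 100.0%) US and 39/40 (86.8% to 99.9%) OUS, which shows plainly how little can be said.
- Use the unadjusted and adjusted contrasts together as supportive evidence on poolability, and do not attribute a one-covariate result to that covariate alone.

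The cost is SAP wording and one extra adjusted contrast to report. The named covariates are already in the plan, and no patients or procedures are added. Section 9.2 keeps device results in a separate file until data lock, so the contrast can still be specified blind; added after the files are merged, it would be post hoc.

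### Section 9.6 judges covariate effects and poolability by the covariate-by-reference interaction, which misses offsetting sensitivity and specificity shifts and has almost no power for a specificity difference alone

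*Combined protocol and SAP*

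**What the plan says.** The overview of section 9.6 says that "possible covariates, will be assessed to determine the impact on the general applicability of results from this study". The subsection on covariates and poolability opens with "The effect of the following covariates will be examined on Device accuracy". The covariates are age, gender, site within each region, region and pre-test probability.

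Two of them carry a named purpose. For site: "This is a test of site poolability within US and OUS separately". For region: "Region (US, OUS), which is a test of poolability of the US and OUS populations". In the site analysis, "enrolling sites with at least 20 subjects will be included separately", and smaller sites are merged into one category.

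Each covariate is entered alone in a logistic model with the Device result as outcome and the covariate, the reference standard and their product as terms. The stated reading is "In this model we are interested in the Cov*Reference interaction, whereby a significant result indicates that Device performance relative to Reference Standard is affected". The section gives no role to the covariate main effect, plans no joint test, sets no significance level, and asks for no sensitivity, specificity or NPV by region or site.

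**The concern.** In this model the covariate main effect is the difference among reference-negatives, that is, in specificity. The main effect plus the interaction is the difference among reference-positives, that is, in sensitivity. The interaction by itself is neither. It is the difference between the two, the log ratio of diagnostic odds ratios. Two separate problems follow.

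- **Structural.** If sensitivity falls and specificity rises by the same amount on the logit scale, as when the effective cut-off differs between populations or laboratories, the interaction is zero however large the trial.
- **Power.** A change in specificity alone does move the interaction, but the term's precision is set by the false negatives, of which very few are expected. The nearly 3,000 PE reference-negatives hardly help.

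The co-primary goals are judged on pooled data, and this model is the plan's named check that pooling is reasonable. A regional difference in accuracy could therefore go unflagged, and the general-applicability statement would rest on a test that could not have seen it.

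**Working it through.** **Inputs from section 9.5.** PE: 3,054 enrolled, with 79 US and 42 OUS reference-positives (uncleaned). "US prevalence of reference-positive = 3.4"%; OUS 5.7%. "D-Di XL sensitivity = 98"%; NPV 99.6%. DVT: 69 US and 46 OUS positives planned, prevalences 5.3% and 8.1%.

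**The plan's own figures.** The documents give no figure for the poolability test. The sample size does reproduce: with 115 positives the exact lower limit reaches 0.90 from 110 true positives, and power at 98% sensitivity is 97.1%, which satisfies the stated bound of at least 90%. For PE, 75/0.034 = 2,206 and 40/0.057 = 702. For DVT, 69/0.053 = 1,302, not the printed 1,032; 1,302 + 568 = 1,870 matches the stated total, so 1,302 is used here.

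**Assumptions.** Two-sided 5% level. PE negatives 2,245 US and 688 OUS (79/0.034 = 2,324 US subjects, leaving 730 OUS). DVT negatives 1,302 − 69 = 1,233 and 568 − 46 = 522. The plan gives no specificity. Its other figures imply Sp = [NPV/(1 − NPV)] × (1 − Se) × p/(1 − p) = 4.98 × p/(1 − p), about 18% to 30% for PE and 28% to 44% for DVT. A wider range was also run.

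**Step 1, the structural zero.** With Se and Sp by region,

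d = [logit Se(US) − logit Se(OUS)] − [logit(1 − Sp(US)) − logit(1 − Sp(OUS))]

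For 98%/60% against 90%/89.1% (Se/Sp): [3.892 − 2.197] − [−0.405 − (−2.101)] = 1.695 − 1.696 = −0.001. Both measures differ clearly, yet the interaction is nil.

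**Step 2, where the variance comes from.** Take sensitivity 98% in both regions and specificity 40% US, 50% OUS. Expected false negatives are 0.02 × 79 = 1.58 and 0.02 × 42 = 0.84. The variance of d is the sum of reciprocal expected cell counts:

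- false negatives: 1/1.58 + 1/0.84 = 0.633 + 1.190 = 1.823
- the other six cells together: about 0.045

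The SE is √1.868 = 1.37, and the false-negative cells supply 1.823/1.868 = 97.6% of the variance. The effect is 0.41, or 0.41/1.37 = 0.30 SE. The chance that at least one region has no false negative, leaving no finite maximum-likelihood interaction, is 1 − (1 − 0.98^79)(1 − 0.98^42) = 54%.

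**Step 3, rejection rates by region** (20,000 simulations each, likelihood-ratio tests):

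| Scenario (Se/Sp, US vs OUS) | Interaction | Specificity | Joint 2-df |
|---|---|---|---|
| PE equal, 98/40 | 6% | 5% | 5% |
| PE offsetting, 98/60 vs 90/89.1 | 7% | 100% | 100% |
| PE offsetting, 98/40 vs 95/63.2 | 7% | 100% | 100% |
| PE specificity only, 40 vs 50 | 5% | 99.5% | 99% |
| PE specificity only, 40 vs 46 | 5% | 80% | 72% |
| DVT offsetting, 98/60 vs 90/89.1 | 5% | 100% | 100% |
| DVT specificity only, 40 vs 50 | 7% | 97% | 95% |

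At 20% vs 30%, within the range the plan's figures imply for PE, the interaction rejects in about 8%. A Wald test of the interaction does worse: 0.01% for PE 40 vs 50, counting a zero cell as not significant.

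**Step 4, sensitivity alone (PE).** For 98% vs 90%: interaction 52%, Fisher 50%, Firth 51%. For 98% vs 95%: 19%, 14% and 14%. Neither approach is powerful.

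**Step 5, sites.** Twenty subjects yield 20 × 0.034 = 0.7 expected positives (PE US) up to 20 × 0.081 = 1.6 (DVT OUS). The chance of none is 0.966^20 = 50% (PE US), 0.943^20 = 31% (PE OUS), 0.947^20 = 34% (DVT US) and 0.919^20 = 18% (DVT OUS). A site with none adds nothing to the interaction test, though its negatives could still be compared. The next figures assume eight equal US sites (4,000 simulations). Specificities alternating between 35% and 45% are flagged in 0.3% by the site interaction and in 96% by a specificity comparison. One site at 70% sensitivity with the others at 98% is flagged in 37% by the interaction and in 54% by an exact comparison of false negatives. The interaction and exact rates use trials with at most eight US false negatives (94–100% of trials).

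**The case against.** The algebra is not in dispute; the objections concern reading and weight.

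- The section names a term of interest. It does not forbid reporting the main effect, calls the model a test of poolability rather than the only one, and never says that non-significance means the data may be pooled. This is right, so the consequence is inferred from the stated reading. But no other term is given any reading.
- The interaction vanishes only for equal logit shifts. With PE sensitivity 98% vs 90%, it rejects in 51% of trials when specificity is 40% in both regions, 41% for 40% vs 45%, 33% for 40% vs 50% and 20% for 40% vs 60%. Partial offsets therefore erode power rather than remove it. This stands, and it also shows the test weakening as the regions diverge further.
- The larger offsetting example would often fail anyway. The sensitivity goals need 116 of 121, reached in 48% of trials at 98% US and 90% OUS. At 98% and 95% they are met in 84%, so the milder regional difference would usually pass.
- For sensitivity alone by region, separate tests gain nothing. The gain is in specificity, a secondary measure with little influence on NPV at these prevalences, and in joint shifts. This stands and limits the weight of the point.
- Section 9.1 provides for separate PE and DVT SAPs, which are not among the documents and may say more. The specificities and the eight-site layout are assumptions.

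**Conclusion.** The concern holds. The interaction cannot detect a shift in both measures that is equal in log-odds, and has about 5–8% power for a 10-point specificity difference by region at 98% sensitivity, against 97% or more for a direct comparison in reference-negatives. The direction does not depend on the assumed specificities: low power persists at the 20–30% implied for PE. The exact percentages do depend on them, on the inferred split of PE negatives and, for sites, on the assumed layout.

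The co-primary success decision is untouched. What is weakened is the evidence for pooling regions and sites and for general applicability. The change should be made, but it does not stand in the way of the primary analysis.

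**What to change.** In the protocol or in the PE and DVT SAPs, before data lock:

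1. For each covariate, including region and site, assess the effect on the Device result in reference-negatives by ordinary logistic regression, and separately in reference-positives by exact or Firth logistic regression. For site, make the second an exact comparison of false negatives, within US and OUS separately.
2. Keep the interaction or a joint two-degree-of-freedom test only as an overall screen.
3. Report sensitivity, specificity and NPV by region with exact 95% intervals, and read the sensitivity comparison from the intervals.
4. Judge specificity differences by size as well as p-value, since small ones will be significant (40% vs 46% in about 80% of PE trials).
5. Label the tests exploratory, state in advance what a flagged difference leads to (for example, regional or site estimates beside the pooled ones), and state that non-significance alone does not establish poolability.

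The cost is SAP wording and a few lines of SAS on variables the trial collects anyway. The drawbacks are more exploratory tests and sensitivity comparisons that stay imprecise: 41 of 42 OUS positives would give 87.4% to 99.9%.
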